4.6.2 Adverse Events of Special Interest

The AESIs will include the following:

- Endophthalmitis,
- Ischemic optic neuropathy,
- Intraocular inflammation; any case of uveitis, retinal vasculitis, or retinal occlusive vasculitis,
- IOP \geq 30 mmHg at 30 minutes post injection deemed clinically significant by Investigator,
- Transient loss of light perception immediately after injection,
- Elevation of IOP post-injection requiring surgical/procedural intervention (i.e., paracentesis),
- BCVA decrease \geq 30 letters from ISEE2009 Month 1 Visit,
- Choroidal neovascularization (exudative or nonexudative),
- Macular oedema/cysts.

AESIs are TEAEs on SE. Both the AESI electronic case report form (eCRF) data and statistical programs will be used to identify AESI events. And the identification rules will be prespecified and documented in the TLF specifications.

The number and percentage of participants with AESIs within each AESI category will be summarized for each cohort. A listing will also be provided.

4.7 Subgroup Analyses

There will be no subgroup analyses.

4.8 Interim Analysis

There will be no interim analysis.

4.9 Sample Size Determination

Approximately 280 participants will be enrolled. This was based on the number of currently enrolled patients in study ISEE2008 (GATHER2) who completed study ISEE2008 through the Month 24 visit.

4.10 Additional Conventions

4.10.1 Analysis Windows

Study Day for analysis windows will be calculated as: Date of visit/assessment – first dose of study drug in this study + 1.

The assignment of analysis visit will be consistent across all by-visit analysis datasets, and will follow the respective step-by-step algorithm:

- All assessment visits will be windowed, per the below tables, regardless of SE/FE, scheduled/unscheduled status, injection date, or pre/post-injection status.
- Baseline derivations will follow the definitions as stated in Section 4.1.

An analysis flag will be created for each record by following rules.

- **General Rules for Analysis Flags**
 - Scheduled visits falling into their respective analysis window will be prioritized over unscheduled visits.
 - If multiple observations still exist, the observation closest to the scheduled day will be selected for the analysis visit.
 - If there are two observations that have the same distance from the scheduled day, the value that is after the scheduled day will be selected for the analysis visit.
 - If more than one observation (excluding OE/IOP observation) is made on the same day, an average value for continuous measurement, or the worst value for categorical measurement, will be used for the analysis visit.
 - Any additional rules will be prespecified and documented in the TLF specifications.
- **Additional Rules for OE/IOP Analysis Flags except those in the Analysis Visit Month 18**
 - The OE/IOP records on a visit falling into its respective analysis window and with at least one SE ACP pre-injection and one SE ACP post-injection records will be firstly selected.
 - If there are no OE/IOP records satisfying the first rule, the records on a visit (whether scheduled or unscheduled) and with at least one SE ACP pre-injection and on SE ACP post-injection records will be selected.
 - If there is no OE/IOP records satisfying the above two rules, the records will be selected from a visit day (whether scheduled or unscheduled) that contain at least one pre-injection or one post-injection record to separately summarize the pre-injection and post-injection IOPs.
 - The closest OE/IOP observation to the target time will be selected for analysis.
 - If both Tonopen and Goldmann measurement are recorded available at the same time per CRF, the Goldmann measurement will be prioritized.

Listings will include all scheduled, unscheduled, and early withdrawal data.

The definitions of analysis visit by different assessment frequency are described in the table below.

Table 2 Analysis Visit for Monthly Assessments

Analysis Visits	Scheduled Day in Protocol ^a (Study Day)	Analysis Windows ^b (Study Day)
Month 1 (Baseline)	1	≤1
Month 2	30	2-45
Month 3	61	46-75
Month 4	91	76-106
Month 5	122	107-136
Month 6	152	137-166
Month 7	183	167-197
Month 8	213	198-227
Month 9	244	228-258
Month 10	274	259-288
Month 11	304	289-319
Month 12	335	320-349
Month 13	365	350-379
Month 14	396	380-410
Month 15	426	411-440
Month 16	457	441-471
Month 17	487	472-501
Month 18	517	≥502
^a Calculated as: $30.4375 \times (\text{Month Number}-1)$ and rounded to integer. ^b Lower bound are calculated as: 
 Scheduled Day – (Day Difference between Current and Previous Scheduled Visits)/2 and rounded to integer since Month 2. Upper bound is calculated as: 
 Lower Bound for Subsequent visit – 1 since Month 2. 		

Table 3 Analysis Visit for Half-yearly Assessments

Analysis Visits	Scheduled Day in Protocol ^a (Study Day)	Analysis Windows for FA and OE (FE) ^{b, c} (Study Day)	Analysis Windows for Other Assessments except FA and OE (FE) ^b (Study Day)
Month 1 (Baseline)	1	Not Applicable	≤1
Month 6 ^d	152	Not Applicable	2-243
Month 12 ^e	335	2-425	244-425
Month 18	517	≥ 426	≥ 426

FA: Fluorescein Angiography; FE: Fellow Eye; OE: Ophthalmic Examination.
 
^a Calculated as: $30.4375 \times (\text{Month Number}-1)$ and rounded to integer.
 
^b Lower bounds are calculated as:
 
 Scheduled Day – (Upper bound – Scheduled Day) and rounded to integer at Month 6, Scheduled Day – (Day Difference between Current and Previous Scheduled Visits)/2 and rounded to integer after Month 6. 
Upper bound is calculated as:
 
 Lower Bound for Subsequent Visit –1, after Month 1. 
^c There is no FA planned before Month 12. Lower bound at Month 12 is calculated as:
 
Scheduled Day – (Day Difference between Current and Previous Scheduled Visits)/2 and rounded to integer.
 
^d The assessments mapped to Month 6 and occurred before Day 62 will not be selected for analysis.
 
^e The assessments mapped to Month 12 and occurred before Day 168 will not be selected for analysis.
			

Table 4 Analysis Visits for Immunogenicity and PK Assessments

Analysis Visits	Scheduled Day in Protocol (Study Day) ^a	Analysis Windows ^b (Study Day)
Month 1 (Baseline)	1	≤1
Month 2	30	2-60
Month 4	91	61-136
Month 7	183	137-273
Month 13	365	274-440
Month 18	517	≥441

^a Calculated as: $30.4375 \times (\text{Month Number}-1)$, rounded to integer.
 
^b Lower bounds are calculated as:
 
 Scheduled Day – (Day Difference between Current and Previous Scheduled Visits)/2 and rounded to integer after Month 2. 
Upper bounds are calculated as:
 
 Lower Bound for Subsequent Visit –1 since Month 2. 		

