7 PROCEDURES

7.1 Refraction, Visual Acuity, and Low Luminance Visual Acuity

Refraction, Vision Testing, and Low Luminance Vision Testing will be performed at all time-points specified in [Section 10.2](#) “Trial Assessments”. BCVA is also required at any other time-point in the event of an ocular AE in the study eye. Retro-illuminated modified Ferris-Bailey Early Treatment Diabetic Retinopathy Study (ETDRS) charts are used starting at 4 meters (see [Appendix 17.1](#)).

When refraction and ETDRS BCVA measurements are required by the trial protocol, these will be performed only by certified VA examiners with access to the previous VA measurement and the previous protocol refraction.

All necessary materials and instructions for these assessments will be provided by Astellas.

These assessments should always be performed in the following order: Refraction, ETDRS BCVA, and Low Luminance Visual Acuity.

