- Ophthalmic exam (SE) and Tonometry (SE): To ensure that the injection procedure has not endangered the health of the eye, the study eye will be assessed immediately (0 to 5 minutes) and 30 minutes after an active injection with an abbreviated ophthalmic exam. A full ophthalmic examination and tonometry will also be performed 30 minutes after injection. Assessments will continue to ensure the central retinal artery (CRA) is adequately perfused and the IOP is within 10 mmHg of the pre-injection value and stable in the opinion of the Investigator.
 - Immediately (0 to 5 minutes) post-injection:
 - Examine the gross visual function of the SE: CF, hand motion, light perception, no light perception
 - Perform direct visualization to:
 - Verify the status of the CRA: CRA is perfused and not pulsating, CRA is perfused and pulsating, CRA is pulsating, or CRA is closed.
 - Verify the retina is attached and there are no new intraocular hemorrhages.

- At 30 minutes post-injection:
 - If no CF at the previous measurement examine the gross visual function of the SE
 - Perform direct visualization to:
 - Verify the status of the CRA: CRA is perfused and not pulsating, CRA is perfused and pulsating, CRA is pulsating, or CRA is closed.
 - Verify the retina is attached and there are no new intraocular hemorrhages.
 - Perform full ophthalmic examination
 - Measure IOP
- Continue beyond 30 minutes post-injection until the CRA is adequately perfused and IOP is within 10 mmHg of the pre-injection value and is stable in the opinion of the Investigator.

Month 2 (±7 days)

- **Pre-Injection:**
 - Urine pregnancy test (if applicable)
 - Immunogenicity and PK sampling
 - Refraction
 - BCVA (4 meters) using ETDRS chart (SE)
 - Tonometry (SE)
 - Full ophthalmologic examination (SE)
 - Optical coherence tomography (SE)
 - Treatment with IVT avacincaptad pegol 2 mg
- **Post-injection:**
 - Ophthalmic exam (SE) and Tonometry (SE): Following same procedures as outlined at Month 1.

Month 3 (±7 days)

- **Pre-Injection:**
 - Urine pregnancy test (if applicable)
 - Refraction
 - BCVA (4 meters) using ETDRS chart (SE)
 - Tonometry (SE)
 - Full ophthalmologic examination (SE)

- Optical coherence tomography (SE)
- Treatment with IVT avacincaptad pegol 2 mg
- **Post-injection:**
 - Ophthalmic exam (SE) and Tonometry (SE): Following same procedures as outlined at Month 1.

Month 4 (±7 days)

- **Pre-Injection:**
 - Urine pregnancy test (if applicable)
 - Immunogenicity and PK sampling

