4.5 Exploratory Endpoint(s) Analysis

The exploratory endpoints are ophthalmic findings. All the assessments will be mapped to a scheduled visit. The mapping rule is provided in Table 2 for BCVA, OE and IOP and Table 3 for LLVA.

Best Corrected Visual Acuity (BCVA)

The score and the change from baseline of BCVA (ETDRS letters) at each analysis visit will be summarized descriptively by cohort for the FAS.

Low Luminance Visual Acuity (LLVA)

The score and the change from baseline of LLVA (ETDRS letters) at each analysis visit will be summarized descriptively by cohort for the FAS.

Low Luminance Deficits (LLD)

The score and the change from baseline of LLD (ETDRS letters) at each analysis visit will be summarized descriptively by cohort for the FAS, where LLD is calculated by the difference of BCVA and LLVA at a same visit.

Intraocular Pressure (IOP)

Baseline IOP is the pre-injection IOP value before the first study drug administration in this study.

Pre-injection IOP is defined as the last IOP value before an injection on a visit with injection (whether ACP or other treatment) or the last IOP value on a visit without an injection.

Post-injection IOP is defined as the IOP value after one injection that is closest in time to the protocol-specified post-injection timepoint (but at least 30 minutes post-injection).

Pre-injection and post-injection IOPs at each analysis visit will be summarized descriptively by cohort for the SAF with in one table. The number and percentage of participants in categories of pre-injection IOP value (≤ 21 mmHg, 22-29 mmHg, 30-34 mmHg, ≥ 35 mmHg) will be summarized at each analysis visit for each cohort.

The change from baseline of pre-injection IOPs will be summarized at each analysis visit for each cohort.

Change of IOP at each analysis visit is the difference between the post-injection and pre-injection IOPs. Change of IOP at each analysis visit will also be summarized descriptively for each cohort. The number and percentage of participants in categories of change of IOP (≤ 0 mmHg, 1-5 mmHg, 6-10 mmHg, >10 mmHg) will be summarized at each analysis visit for each cohort.

The number and percentage of participants who experienced the following events will be summarized for each cohort. The events are:

- Either pre-injection or post-injection IOP ≥ 35 mmHg,
- Had a paracentesis and
- Received IOP-lowering medications.

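### SAP 4.10.1 can average a post-injection BCVA, taken because of an ocular adverse event, with the scheduled pre-injection BCVA of the same dosing visit

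*SAP*

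**What the plan says.** SAP 4.10.1 first assigns every record to an analysis window, "regardless of SE/FE, scheduled/unscheduled status, injection date, or pre/post-injection status". It then lists general rules for choosing the value to analyse:

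1. "Scheduled visits falling into their respective analysis window will be prioritized over unscheduled visits".
2. "If multiple observations still exist, the observation closest to the scheduled day will be selected for the analysis visit".
3. If two records are equally far from the scheduled day, the later one is taken.
4. "If more than one observation (excluding OE/IOP observation) is made on the same day, an average value for continuous measurement" is used; for categorical data the worst value is taken.

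Ophthalmic examination and IOP have additional rules that recognise pre- and post-injection records. BCVA has none. The section leaves any further rules to the TLF specifications.

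Protocol 10.2 lists BCVA among the pre-injection procedures at every dosing visit. Protocol 7.1 adds: "BCVA is also required at any other time-point in the event of an ocular AE in the study eye"; footnote k of the Study Assessments table (Section 3) says the same. Protocol 10.2 makes the routine vision check straight after injection a coarse one: "Examine the gross visual function of the SE: CF, hand motion, light perception, no light perception".

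SAP 4.5 summarises BCVA, LLVA and low luminance deficit (LLD) by visit, "where LLD is calculated by the difference of BCVA and LLVA at a same visit". SAP 4.1 defines baseline as the last value before the first dose in this study.

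**The concern.** A BCVA taken before the injection and one taken afterwards because of an adverse event are not replicates. The second follows dilation, topical anaesthetic, povidone-iodine and a 0.1 mL injection, and Appendix 17.2 itself tells patients to expect some blurring. Their mean describes neither the eye's vision on arrival nor the size of the acute change.

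The error would be selective. It can arise only in eyes with an ocular adverse event, and only after baseline, because a post-injection value cannot enter baseline. LLD would combine a mixed BCVA with an LLVA that is scheduled only before injection.

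There is also a safety-detection question. A BCVA decrease of at least 30 letters from Month 1 is an adverse event of special interest (AESI). SAP 4.6.2 uses statistical programs as well as eCRF data to identify such events, and does not say whether the programs read individual or averaged BCVA.

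**Working it through.** The plan gives no figure for this effect, so there is none to reproduce. The check traces the rules and then applies simple arithmetic.

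**Rule trace for two BCVA values on one dosing day**

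- *Repeat recorded under the scheduled visit.* Rule 1 ranks visits, and both values belong to the same scheduled visit. Rules 2 and 3 use distance in days, which is equal for two records on one day. Rule 4 then applies and averages them.
- *Repeat recorded as an unscheduled visit.* Rule 1 keeps the scheduled value and nothing is averaged.

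The SAP does not say which of these applies to a same-day repeat.

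**Visits exposed**

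- BCVA: injections run from Month 1 to Month 17 (Protocol 9.1.2). Month 1 is protected by the baseline definition and Month 18 has no study injection. That leaves Months 2 to 17, which is 16 visits.
- LLD: LLVA is taken at Months 1, 6, 12 and 18 (Protocol Section 3). Removing Months 1 and 18 leaves Months 6 and 12.

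**Size in one eye.** Let P be the pre-injection score and D the acute drop.

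- Averaged visit BCVA = (P + P − D)/2 = P − D/2.
- LLD = BCVA − LLVA, so LLD also falls by D/2.
- Example with assumed values P = 60, post-injection 40, LLVA 35: BCVA = (60 + 40)/2 = 50 instead of 60; LLD = 50 − 35 = 15 instead of 60 − 35 = 25.
- D = 5, 10, 15, 20 or 30 gives an error of 2.5, 5, 7.5, 10 or 15 letters.

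**Size in a cohort mean.** If a fraction f of eyes at a visit has an averaged repeat, the mean shifts by −f × D/2. Both f and D are assumptions, because the documents give neither.

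| f | D = 5 | D = 10 | D = 20 | D = 30 |
|---|---|---|---|---|
| 1% | −0.025 | −0.05 | −0.10 | −0.15 |
| 2% | −0.05 | −0.10 | −0.20 | −0.30 |
| 5% | −0.125 | −0.25 | −0.50 | −0.75 |

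**AESI threshold.** If the pre-injection score is unchanged from Month 1, an acute fall of 30 letters appears as 30/2 = 15 after averaging. A program reading averaged values would need a fall of 2 × 30 = 60 letters to reach the threshold.

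**The case against.** The strongest answer is rule 1. The extra BCVA is required at time-points other than the indicated visits, which fits an unscheduled record. If it is filed that way, the scheduled pre-injection value is used and no error arises. The phrase "scheduled/unscheduled status, injection date, or pre/post-injection status" governs assignment to a window, not which record is chosen. This stands, and it makes the point conditional. It does not remove it: rule 1 ranks visits, not measurements, and a test repeated during a dosing visit can naturally be filed under that visit.

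Three stronger readings are tempting, and the documents do not support them.

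- *A reader might infer that averaging will happen whenever an adverse event is seen after injection.* No section names a same-day post-injection ETDRS BCVA, and the routine check is gross visual function. A repeat is possible and not excluded, but it is not established. The CRF layout and the TLF specifications, which might settle the matter, are not available.
- *A reader might take the 13% conjunctival hemorrhage and 9% increased IOP in Protocol 4.6 as a guide to frequency.* These are percentages of adverse reactions reported up to 12 months. They give no onset day, no per-visit rate, no letter loss and no rate of repeat testing.
- *A reader might infer that LLD is affected throughout, or that acute vision loss is hidden.* LLD is exposed at two visits only. Adverse events are the primary endpoint, the 30-letter AESI is also reported by the investigator on a questionnaire in an expedited manner, and listings keep all records.

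It is also fair that BCVA is exploratory, that no hypothesis is tested, and that a sub-letter shift in a mean would change no decision.

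**Conclusion.** Wrong as written, low severity. A stated rule, not merely a missing detail, can produce an incorrect visit value, and only in eyes with an ocular adverse event. The condition is that a post-injection BCVA is taken on a dosing day and recorded under the scheduled visit; filed as unscheduled, it is dropped. A by-visit result should not depend on that filing choice.

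In an affected eye the error is half the acute drop, for BCVA at Months 2 to 17 and for LLD at Months 6 and 12. The cohort-mean shift is at most 0.75 letters for f up to 5% and D up to 30, both assumed, so cohort summaries are unlikely to mislead. The reasons to act are the individual values and the unstated input to program-based AESI detection. The plan does not say that detection runs on averaged values; it leaves this open.

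**What to change.** Amend SAP 4.10.1 to state that:

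- on injection days, by-visit BCVA, LLVA and LLD use the scheduled pre-injection measurement, however a repeat is recorded; at Month 18 or early withdrawal, the scheduled measurement is used;
- same-day averaging of these measures is limited to replicates taken before the injection;
- BCVA taken after an injection or because of an adverse event is kept out of the by-visit summary and identified separately in the listings.

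In SAP 4.6.2, or the TLF specifications it refers to, state that program-based detection of a BCVA decrease of at least 30 letters uses individual values, not averaged ones.

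The cost is a few lines of text and a programming filter, provided that test time or pre/post-injection status can be identified in the collected records. No new data or visits are needed.

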10.3 Development of CNV During the Trial

If the Investigator suspects the development of CNV in the study eye, or if the subject has > 5 ETDRS letters of VA loss between the current visit and the immediate past visit where VA was assessed, the diagnosis must be assessed with fundus photography, FA and OCT and **confirmed by the Duke RC prior** to initiating anti-VEGF treatment in the study eye. The trigger for imaging studies should be the Investigator's suspicion of CNV. VA change alone does not constitute a requirement for imaging studies.

For patients who develop CNV in the study eye and the diagnosis is confirmed by the Duke RC during the trial, the study eye should be treated with either Lucentis® (ranibizumab), Eylea® (aflibercept), or Vabysmo® (faricimab) per their label.

If the Investigator plans to administer the anti-VEGF agent on the day of the diagnosis, the Duke RC will confirm the diagnosis within 1 hour after receiving the images. If the anti-VEGF agent and avacincaptad pegol are administered in the SE on the same day, avacincaptad pegol should be administered first, and the anti-VEGF administered second. The anti-VEGF agent may NOT be administered after the avacincaptad pegol injection until the IOP is ≤ 21 mmHg or within 5 mmHg of the baseline IOP on that day (i.e., the "baseline" IOP is the pre-injection IOP before the avacincaptad pegol administration on that day). If the IOP is **not** ≤ 21 mmHg or within 5 mmHg of the baseline IOP, the IOP should continue to be monitored until it is ≤ 21 mmHg or within 5 mmHg of the baseline IOP before proceeding to the anti-VEGF injection.

For the anti-VEGF agent administration, it is **mandatory** that, the same injection preparation and administration protocol specified for the avacincaptad pegol administration be followed by the ophthalmologist. Please refer to [Appendix 17.2](#) Intravitreal Administration Protocol; for example, the use of aseptic technique, sterile gloves, anesthesia, eye speculum, and povidone-iodine are required.

IVT injection is contraindicated in patients with active ocular or peri-ocular infections and in patients with active intraocular inflammation.

The subject will continue with the study treatment (avacincaptad pegol) as scheduled.

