2 STATISTICAL HYPOTHESES

No statistical hypotheses will be tested.

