4.2.3 Demographic and Other Baseline Characteristics

Demographics will be summarized descriptively by cohort for the FAS. The variables to be summarized include but not limited to:

- Sex,
- Age, Age Categories (50 to <65, 65 to 74, 75 to 84, ≥85), European Union Drug Regulating Authorities Clinical Trials Database (EudraCT) age categories (<65, ≥65 to <85, ≥85),
- Race,
- Ethnicity.

Other baseline characteristics of SE will be summarized descriptively by cohort in separate tables. These baseline characteristics include the followings:

- Visual acuity, including but not limited to BCVA (Early Treatment Diabetic Retinopathy Study [ETDRS] letters), LLVA (ETDRS Letters) and LLD,
- Ophthalmic exam (OE), including but not limited to motility, lids/lacrimonal/lashes, conjunctiva/sclera, cornea, anterior chamber activity, cells, iris, pupils, lens status, vitreous haze, vitreous hemorrhage, posterior vitreous detachment, optic nerve, macula, retinal vessels, and peripheral retina,
- Tonometry,
- Fundus Autofluorescence (FAF) imaging measurements, including but not limited to localization of hypo FAF, multifocal geographic atrophy, temporal peripapillary atrophy, area of geographic atrophy and size of geographic atrophy.

A listing of demographic and other baseline characteristics will be provided.

Prior ocular history is defined as all ocular events prior to the first administration of the study drug in this study, including the prior ocular history events of the parent study ISEE2008.

The prior ocular history is coded in Medical Dictionary for Regulatory Activities (MedDRA) and will be summarized by System Organ Class (SOC) and Preferred Term (PT), by cohort, for Study Eye (SE) and Fellow Eye (FE) separately. A listing of prior ocular history will also be provided.

Medical history (excluding ocular history) is defined as all non-ocular medical events prior to the first administration of the study drug in this study, including the non-ocular medical history events of the parent study ISEE2008. The medical history (excluding ocular history) is coded by MedDRA, and will be summarized by SOC and PT, by cohort. A listing of medical history will also be provided.

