The number and percentage of injections with the following events will be summarized for each cohort. The events are:

- Either pre-injection or post-injection IOP ≥ 35 mmHg,
- Had a paracentesis.

Mean of pre-injection IOPs change from baseline and post-injection IOPs change from pre-injection will be plotted over time separately.

Ophthalmic Examination (OE)

The following OE variables will be analyzed for the SAF by a shift table (Normal/Abnormal/Missing) from Baseline to Month 18/End of Study (Early Withdrawal):

- Motility,
- Lids/Lacrimal/Lashes,
- Conjunctiva/Sclera,
- Cornea,
- Iris,
- Pupils,

- Posterior Vitreous Detachment,
- Optic Nerve,
- Macula,
- Retinal Vessels.

Participants with a change in lens status (aphakic, pseudo-phakic, phakic; if phakic, nuclear/PSC/cortical 0, 1, 2, 3, 4) will be listed for SE and FE.

Geographic Atrophy Area

Change from baseline in Geographic Atrophy Area of SE will be summarized descriptively at each analysis visit for each cohort.

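### The exploratory eye-examination and eye-pressure summaries under-represent transient safety findings; they need a worst-value examination shift, all-readings pressure counts and a clear early-withdrawal rule

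*SAP*

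**What the plan says.** **Examination.** SAP 4.2.3 names 16 examination variables for the baseline summary, among them "anterior chamber activity, cells, iris, pupils, lens status, vitreous haze, vitreous hemorrhage, posterior vitreous detachment". After baseline, SAP 4.5 says that a set of OE variables "will be analyzed for the SAF by a shift table (Normal/Abnormal/Missing) from Baseline to Month 18/End of Study (Early Withdrawal"). That set has ten members. Changes in lens status are listed separately. Protocol 11.1 names the ophthalmic examination as an exploratory endpoint, and Protocol 11.4.1 promises summary statistics for every endpoint.

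**Pressure.** In SAP 4.5, "Pre-injection IOP is defined as the last IOP value before an injection on a visit with injection"; at a visit without an injection it is the last value of that visit. Post-injection IOP is the single value nearest the scheduled post-injection time, and not earlier than 30 minutes. The event tables count participants, and then injections, with either of these values at 35 mmHg or more. They also count paracenteses.

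**Windows and record selection.** SAP 4.10.1 assigns every visit to a month by study day. Table 2, which governs monthly OE and IOP, gives Month 18 to Day 502 onward. At all analysis visits except Month 18, visits "with at least one SE ACP pre-injection and one SE ACP post-injection records will be firstly selected". Unpaired records come last: "If there is no OE/IOP records satisfying the above two rules, the records will be selected from a visit day (whether scheduled or unscheduled").

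The study is descriptive throughout: "No statistical hypotheses will be tested".

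**The concern.** This is an open-label safety study with no concurrent control, and its primary endpoint is investigator-reported adverse events. Under Protocol 12.1 an objective finding becomes an adverse event only if it is symptomatic, needs treatment, changes dosing, has a serious outcome, or is judged to be one by the Investigator or Sponsor. The examination and pressure data are the measured cross-check on that judgement.

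The cross-check has limited reach. An inflammation that comes and goes between visits will rarely be present at one final exam, and its direct signs are not in the table at all. A pressure peak that is not the defined reading is not in the 35 mmHg count. A reader of the study report could take a quiet OE shift table as confirming the adverse-event tables when it had little chance of showing otherwise.

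**Working it through.** **1. The windows reproduce.** Scheduled day = 30.4375 × (Month − 1); lower bound = 30.4375 × (Month − 1.5), rounded; upper bound = next lower bound − 1.
- Month 7: 30.4375 × 6 = 182.6, so Day 183. Lower bound 30.4375 × 5.5 = 167.4, so 167. Month 8 starts at 30.4375 × 6.5 = 197.8, so 198. Month 7 is therefore 167–197, as in Table 2.
- Month 18: 30.4375 × 17 = 517.4, so Day 517. Lower bound 30.4375 × 16.5 = 502.2, so 502, as in Table 2.

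Every lower bound from Month 3 to Month 18 matches. Starting from rounded scheduled days shifts four of them (Months 7, 9, 14, 16) by one day. That is a rounding variant, not an error.

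**2. OE variables.** 16 at baseline − 10 in the shift = 6 absent. Lens status is listed, which leaves 5 with no planned post-baseline summary: anterior chamber activity, cells, vitreous haze, vitreous hemorrhage and peripheral retina. The first three are direct signs of inflammation. Protocol 7.3 has the anterior chamber and vitreous examined at every scheduled exam.

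**3. OE timing.** Exams run at Months 1 to 18, so there are 17 post-baseline visits, of which the shift uses one: 1/17 = 5.9%. Month 18 has no injection and falls 517 − 487 = 30 days after the last scheduled one.

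For illustration, assume an episode of fixed length *d* with onset uniform over 517 days. The chance that it is present at the Month 18 exam is about *d*/517. The chance that it is present at one or more monthly exams is about *d*/30.4375, capped at 1. The lengths are assumptions; the documents give none.

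| Episode length (days) | Present at Month 18 exam | Present at one or more monthly exams |
|---|---|---|
| 14 | 2.7% | 46% |
| 28 | 5.4% | 92% |
| 90 | 17.4% | 100% |

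If onset clusters soon after injections, short episodes are less likely to last until the next monthly exam, and unscheduled exams matter more.

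**4. Early withdrawal.** An exam on Day 200 falls in 198–227 and maps to Month 8. Under the window rule the participant has no Month 18 record and would be Missing in the shift. Under the table's label, the same exam is the shift endpoint. Both cannot apply.

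**5. Pressure counts.** Three kinds of recorded reading can fit neither defined value:
- an earlier reading before the injection, if a later one follows (Appendix 17.2 allows pressure-lowering drops before injection);
- a reading before a paracentesis done within the first 30 minutes (Appendix 17.2 requires it on the CRF);
- a higher reading later in the extended monitoring of Protocol 10.2.

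A high reading at an unscheduled visit is also missed if only flagged visits feed the counts, and SAP 4.5 does not say. The categories 30–34 and ≥ 35 mmHg apply to pre-injection values only. Post-injection IOP of 30 mmHg or more is counted only as an AESI, and only when the Investigator deems it clinically significant.

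**6. Paired-visit preference, in the Month 7 window.**
- Injection withheld on Day 183, no other visit: the fallback rule selects that visit.
- Withheld on Day 183, injected at an unscheduled visit on Day 195: Day 195 replaces Day 183. The general scheduled-first rule alone would keep Day 183.
- Injected on Day 183, unscheduled visit on Day 190: Day 183 is selected under either rule.

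Only the second case changes. It needs re-injection within 197 − 183 = 14 days of an on-target visit, or 197 − 176 = 21 days if that visit was 7 days early (one day more in some windows).

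**The case against.** The strongest reply is that these events are tabulated elsewhere. SAP 4.6.2 counts intraocular inflammation, endophthalmitis, clinically significant post-injection IOP of 30 mmHg or more, and pressure rises needing intervention as AESIs by cohort, identified from both the eCRF and programs. TEAEs are the primary analysis, and raised IOP counts as ocular. SAP 4.5 counts participants with a paracentesis or pressure-lowering medication, so a treated spike is not lost. By-visit tables show the maximum of the selected values, and listings keep everything. The 30-minute reading follows the protocol's own schedule. The affected tables are exploratory.

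All of this stands and limits the point. It does not close it: AESI and TEAE entries rest largely on investigator judgement, the program rules for AESIs are left to the TLF specifications, and a listing gives no rate.

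Three stronger readings are tempting, and the documents do not support them.
- A reader might infer that pressure spikes and inflammation vanish from the safety tables. They do not, for the reasons above.
- Because "IVT injection is contraindicated in patients with active ocular or peri-ocular infections and in patients with active intraocular inflammation", a reader might infer that the paired-visit preference removes inflamed eyes from the OE shift. The preference is not applied at Month 18, the only post-baseline visit in that shift. Its practical effect is on by-visit IOP tables, which do not measure inflammation.
- A reader might infer that high pressure leads to withheld injections and so to deselected visits. I find no rule that withholds the study drug for high IOP; the limits in Protocol 10.3 concern the anti-VEGF injection given after it. Preferring visits with a post-injection reading also keeps the readings where an injection spike would show.

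On early withdrawal, the fair description is a conflict between two passages, not a settled exclusion.

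**Conclusion.** The point holds in limited form and should be acted on. It does not touch the primary endpoint.

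- **Firm, from the text:** the OE shift uses 1 of 17 post-baseline visits and leaves five variables without any post-baseline table, which falls short of Protocol 11.4.1. The early-withdrawal label and Table 2 conflict.
- **Firm in definition, open in extent:** the 35 mmHg counts rest on single defined readings, and the source visits are not stated.
- **Minor:** the paired-visit preference alters by-visit IOP only when a withheld and an injected visit share a window.

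The percentages for episode length rest on uniform onset and assumed durations; they show direction, not an expected loss. The number of participants affected depends on early withdrawals, paracenteses, repeat readings and withheld injections, for which the documents give no figures.

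**What to change.** 1. Keep the present analysis flags for by-visit summaries only.
2. Add a study-eye OE shift from baseline to worst post-baseline value over all scheduled and unscheduled exams. Include anterior chamber activity, cells, vitreous haze, vitreous hemorrhage and peripheral retina. The shift would then cover 15 of the 16 named variables (lens status is already listed) and draw on up to 17 post-baseline visits.
3. Define the end-of-study shift endpoint as the Month 18 or early-withdrawal exam, whatever its study day.
4. Base the IOP event counts on all recorded study-eye readings, including unscheduled, repeat and pre-paracentesis values, and say so. Add a count at 30 mmHg or more beside the one at 35.

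The cost is SAP wording and a few extra tables from data already collected. Reported counts may rise, because the tables will include readings that the present definitions leave out.
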